9.3 Interview by telephone

The patient will be interviewed by telephone twice by a medical student to answer a questionnaire about health consumption and absenteeism.

9.4 Data

The study coordinator is involved in coordination, collecting and analysing data.

9.5 Stimulation parameters

Setting stimulation parameters will be done by one of the case-managers (specialized nurses), the neurosurgeon or the anaesthesiologist who implanted the device (not blinded).

9.6 Surgery and hospital visits

The period of surgery and defining and adjusting the stimulation parameters will take approximately 2-3 days. After 10 days, the patient returns to the hospital for examination of the wound and removing stitches and test the system (impedances), and calibration of stimulation. After month 1, 2, 4 and 6 the patient will return to the clinic for evaluation and stimulation adjustments. The study neurologist will be seeing the patient on a monthly basis during the blinded part of the study(with the exceptions of visits 3 and 5 months follow-up which can be replaced by telephone calls in case the patient prefers this); this will be on a 3-monthly basis during the second part. During these evaluations the following scores will be taken (in the electronic diary or during an interview): *for details see appendix 24.1*

Protocol: Occipital nerve stimulation in medically intractable, chronic cluster headache CME Protocol number: 10.016 Version 1.11 dd. 26-09-2018 Electronic diary in Promise:

- Medication use
- Frequency of attacks of CH and other headache attacks
- Intensity of attacks: Numeric pain rating scale (only during the 6th and 12th month and 2 weeks before for practice)
- Absenteeism from work
- The awareness of paraesthesias: localisation (coding system) and strength (0= no paraesthesias 10= strongest paraesthesias
- Monthly SF-36

Interview:

- Adverse events; painful stimulation, neck stiffness, uncomfortable feeling of the device, infection, lost sensation of stimulation, when suspected lead migration: X-ray cervical spine
- Patient satisfaction

Before evaluations patients fill in their daily electronic diary, which will be send to our database after every 7 days (the patients will get a reminder per email or telephone). In the case of holiday, or not possessing a computer with internet access or another reason that discourages the patients from filling in the electronic diary, the patient receives a hard copy form of the diary, which can be copied to the electronic diary later.

At 6 and 12 months post randomisation, all patients return to the study neurologist/ study coordinator for the final recording of the headache diary and interview. The patient will be asked at 6 and 12 months follow-up to which group they think they have been randomised in the first 6 months treatment period and if he/she would recommend the treatment to other patients.

After ending the study, the study patients will be able to continue the study treatment on compassionate grounds. This will mean that they will continue to receive treatment at the study centre as is necessary for the ONS.

10.1 Defining stimulation amplitudes

The amplitude of stimulation will be established for each individual patient by determining the patient's individual therapeutic range as described in Trentman et al. (26). They found a mean amplitude for perception of 1.07 V and discomfort of 3.63 V. Stimulation frequency and pulse width will be uniformly held constant at 60 Hz and pulse width at 450 µs. The perception and discomfort amplitude will be defined by increasing the stimulation amplitude in steps of 0.1 V. The head will be in neutral position. The amplitude at which the patient starts feeling paraesthesias is called the perception threshold. The threshold at which the patient does not want the voltage to be increased any further because of painful sensations is designated the discomfort threshold. 100% stimulation is defined as stimulation at 90% of the range between perception and discomfort thresholds. Consequently, 30% stimulation means a stimulation level at 30% of the range between perception threshold and 100% stimulation level. The same goes for the 10%, 20%, 40% and 70% stimulation. Defining these thresholds will be done using a standard method by trained nurses or doctors and will be repeated 3 times, and only accepted if the values differ no more than 20%. The procedure will be repeated until the values differ no more than 20%.

Definitions:

DT: Discomfort threshold PT: Perception Threshold SL_{100%} stimulation: 100% stimulation level

Formula: $SL_{100\%} = PT + 0.9 \text{ x (DT-PT)}$

 $SL_{X\%} = PT + (SL_{100\%} - PT) \times X/100$

Example: PT: 1.0 V and DT: 6.0 V.

 $SL_{100\%} = 1.0 + 0.9 \text{ x} (6.0-1.0) = 5.5 \text{ V}.$

 $SL_{20\%} = 1.0 + (5.5-1.0) \times 20/100 = 1.9 V$

 $SL_{70\%} = 1.0 + (5.5 - 1.0) \times 70/100 = 3.3 V$

10.2 Surgery

Since there will be no trial stimulation, the proposed abdominal location of the Implantable Pulse Generator (IPG) should be discussed with the patient on beforehand. In case of contra indications according to the patient or implanter for placement of the IPG abdominal, another location will be chosen for instance on the buttock. The procedure is performed under general anaesthesia and antibiotic prophylaxis: Cephalozin 1 or 2 g (according to local guidelines) (when the patient is allergic to certain antibiotics, please consult the hospital microbiologist for advice) given half an hour prior to actual surgery. The procedure will be done in two tempi. First the patient is positioned in a prone position with his/her head facing downwards in an adjustable U shaped headrest. After removing hair from the upper neck/lower occipital area using a clipper and disinfecting twice the area from low occipital to the left flank, an incision drape is used when sterile draping is applied to the surgical site. Using fluoroscopy the skin is marked at the level of vertebral arc C1. Here, a small area is infiltrated with a mixture of Lidocain(10mg/ml)/Epinephrine(5mcg/ml), before a small (2 cm) cranio-caudal incision is made. A 2-3 cm diameter subcutaneous pocket is prepared. The Touhy needle is slightly bent and then under fluoroscopic guidance inserted in lateral direction just beneath the skin and outside the fascia. The Quad Plus® (56 cm length; or shorter according to the length of the patient and preference of the implanter) is inserted after the stylet is removed. It is advanced until all electrodes are covered, then the Touhy needle is removed whilst keeping the lead in place. The lead is secured with a Titan anchor® that is fixed to the midline-fascia in the pocket with nonresorbable sutures (Mersilene® 1-0). By slightly pulling the lead the fixation is checked.

On the contralateral side, exactly the same procedure is performed. With the lead passer the lead is then subcutaneously led to the left flank, an in-between incision may

Protocol: Occipital nerve stimulation in medically intractable, chronic cluster headache CME Protocol number: 10.016 Version 1.11 dd. 26-09-2018 be required. The lead is looped at least two sites along the way, to avoid inadvertent damage by possible traction. Finally all wounds are sutured.

In a **second period** the patient is positioned laterally, right side facing down. The surgical area (flank towards left abdomen or buttock where the agreed upon spot is marked for the IPG) is disinfected twice and sterile (incision) drapes applied. A 7-8 cm paraumbilical incision is made at the marked site, a pocket (5x5 cm) is made using blunt dissection (no monopolar cautery allowed) in the subcutaneous fat layer over the abdominal fascia. The incision in the flank is re-opened and a small pocket (3x3 cm) is made there as well. From here the passer is inserted to the abdominal pocket. The lead extensions are pulled through and connected to the leads. The connection is covered by a silicon sheet fixed with nonresorbable sutures. The extension cables are connected to the IPG (VersitrelTM) which is implanted into the pocket and secured with 1 or 2 nonresorbable sutures. The N'visionTM programmer is used to analyse impedances of this neuromodulation system. When there are no system failures, remaining wounds are sutured.

SUMMARY: Low occipital bilateral Quad Plus, midline to laterally directed, secured by titan anchors, connected to Versitrel. No trial stimulation. Suggested stimulation parameters: Pulse width: 450, Amplitude: protocol, Rate: 60.

10.3 Devices used

IMPLANTABLES (Medtronic order nr)if a Versitrel IOG is used: IPG: Versitrel[™] (7427V), Extension cable: Low profile Quad extension cable 10-60 cm, length depends on patient characteristics (7489 10-60), Lead: Pisces Quad® Plus 56 cm (388856) (or a different length), Fixation: Titan Anchor® (3550-39), Versitrel[™] Patient Programmer (7435)

It is also allowed to use the Prime Advanced IPG (37702) with compatible extension cables in stead of the Versitrel IPG, as this IPG the 'newer version' of the Versitrel (7427V) and some implantation sites are more common with this. The most important difference is the more advanced software, which will only matter to the nurse or doctor adjusting the stimulator, because it is easier in use. We don't think the participating patients will be caused disadvantage by using either IPG.

Protocol: Occipital nerve stimulation in medically intractable, chronic cluster headache CME Protocol number: 10.016 Version 1.11 dd. 26-09-2018 IMPLANTABLES (Medtronic order nr) if a Prime Advanced IPG is used: Prime AdvancedTM (37702), Bifurcated extension cable 20-40-60 cm, length depends on patient characteristics (37082-20/-40/-60), Anchor injex bumpy or injex bi-wing (97791 or 97792), Plug (3550-29), 2 Quad-plus electrode 28-33-45-56 cm, length depends on patient characteristics (3888-28/-33/-45/-56), Trialling cable (3555-31), Mystim (97740).

11. Economic evaluation

The objective of the economic evaluation part of this study is to examine whether the delivery of high (100%) stimulation compared to low (30%) stimulation is preferable in terms of costs, effects and utilities from a societal perspective.

11.1 Design and participants

Economic evaluations compare additional costs and additional outcomes of high stimulation compared to low stimulation. This economic evaluation will involve a combination of a cost-effectiveness analysis (CEA) and a cost-utility analysis (CUA). In a CEA effects are presented in clinical outcomes (in our study frequency of CH attacks during the last 4 weeks of the 100% stimulation period and the 30% stimulation period). The primary outcome measure for the cost-utility analysis will be Quality Adjusted Life Years (QALYs), based on the SF-36 utility scores (29-31). In the CUA, the Incremental cost-effectiveness ratio (ICER) will be expressed as the incremental costs per QALY. This economic evaluation will be performed from a societal perspective, which implies that all relevant costs and outcomes will be taken into account. With regard to this research question we hypothesize that the high stimulation is associated with an increased effect, and an increase in quality of life. The time horizon will be the same period as the follow-up period of the double blind part of the main study, 6 months. Costs (the use of resources) will be measured continuously using a (retrospective) questionnaire (6 months); outcomes for the economic evaluation study will be measured at pre-test before random assignment into groups (baseline), and at 6 months.

The second part of this economic evaluation will be a cost-of-illness (COI) study. The objective of this COI analysis is to calculate the societal costs of MICCH in the Netherlands. This prevalence based, retrospectively and bottom-up cost of illness Protocol: Occipital nerve stimulation in medically intractable, chronic cluster headache CME Protocol number: 10.016 Version 1.11 dd. 26-09-2018 study will be performed at baseline using a (retrospective) questionnaire (6 months) and an electronic diary for the use of attack medication.

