There is no established treatment for patients with MICCH. ONS has been used in open label trials with promising results (7;19-22). A prospective, randomised, controlled clinical trial is necessary to assess the efficacy, tolerability and safety of ONS in the treatment of MICCH.

4. Study design

This is a prospective, randomised, double blind, parallel group multi-centre international clinical study to compare the reduction in attack frequency from baseline of occipital nerve stimulation (ONS) in patients with MICCH between two different stimulation conditions: high (100%) and low (30%) stimulation. (see paragraph 10.1)

Active ONS is associated with paraesthesias complicating blinded comparison versus no stimulation. From our own experience with patients treated with ONS, we know that patients might find it difficult to differentiate paraesthesias associated with 100% and 30% stimulation. Recognition of the stimulation intensity would be further complicated by stepwise increasing the stimulation intensity.

Patients will be included for a 3 month baseline period, of which the first month serves for practice only. If the patient still meets the inclusion criteria after this baseline period, he/she will be randomised and scheduled for surgery. Following surgical implantation there will first be a run-in phase of 10 days of 10% stimulation intensity until wound check, followed by a stepwise increase up to either 30% or 100%. Patients in the 100% stimulation arm will receive this intensity for 4 months.

Patients will be assessed every month by the blinded study neurologist. If the patient finds the stimulation painful in between follow-up moments, an extra follow-up moment will be arranged soon and the threshold for discomfort will be defined again. The primary outcome measure is the number of attacks over the last 4 weeks of the double blind 6 month treatment period. Hereafter, in an open extension phase of 6 months, all patients will receive 100% stimulation or the stimulation considered optimal by the patient. The patients will fill in an (electronic) diary during the whole study period.

Rationale design

We estimated the effect of ONS in three Dutch patients. We found that sensation threshold and discomfort threshold can be repeatedly defined and that patients could not distinguish small differences in stimulation.

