The primary outcome measure for the cost-effectiveness analysis will be increase in health status as measured by the CH attacks 4-weekly at 6 months of follow-up of the last month of both treatment arms. Within the cost-utility analysis, utilities will be derived using an indirect preference-based technique. In this technique, the patient's health status will be monthly measured by means of the standard Dutch version of SF-36 and weights, that incorporate preferences from a general population sample, will be used to calculate utilities from the SF-36; the Short Form 6D (SF-6D) (29;31). The SF-36 will be completed monthly in the electronic diary and the cost questionnaire will be completed at baseline and at 6 months follow-up by an interview by telephone. The SF-36 is chosen because it is a widely used quality of life instrument (nationally and internationally), also in the field of headache (38). Utility values can be calculated for these health states, using preferences elicited from a general population, the socalled Brazier algorithm (29). The utility values derived from the Brazier algorithm will be used to compute QALYs. The Brazier algorithm has been established using a general population from the UK (29). The utilities at the time points will be used to compute a QALY score by means of the area under the curve method.

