The ICER will be determined on the basis of incremental costs and effects of high stimulation compared to low stimulation. The cost-effectiveness ratio will be stated in terms of costs per outcome rate, the cost-utility ratio will focus on the net cost per QALY gained. The ICER will be calculated as follows. ICER = (Ci - Cc) / (Ei - Ec), where Ci is the annual total cost of the high stimulation group, Cc is the annual total cost of the low stimulation group, Ei is the effect at one year follow-up for the high stimulation group and Ec is the effect at one year follow-up for the low stimulation group. The robustness of the ICER will be checked by non-parametric bootstrapping (1000 times). Bootstrap simulations will also be conducted in order to quantify the uncertainty around the ICER, yielding information about the joint distribution of cost and effect differences. The bootstrapped cost-effectiveness ratios will be subsequently plotted in a cost-effectiveness plane, in which the vertical line reflects the difference in costs and the horizontal line reflects the difference in effectiveness. The choice of treatment depends on the maximum amount of money that society is prepared to pay for a gain in effectiveness, which is called the ceiling ratio. Therefore, the bootstrapped ICERs will also be depicted in a cost-effectiveness acceptability curve showing the probability that high stimulation is cost-effective using a range of ceiling ratios.

Additionally, to demonstrate the robustness of our base-case findings a multi-way sensitivity analyses will be performed. In the sensitivity analysis uncertain factors of assumptions in the base case analysis will recalculated in order to assess whether the assumptions have influenced the incremental cost-effectiveness ratio (ICER), for example by varying cost-prices and volumes between minimum and maximum (41).

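### The cost-effectiveness effect is a lower-is-better attack count over 4 weeks, with no stated conversion to a benefit and no match to the 6-month cost window

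*Combined protocol and SAP*

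**What the plan says.** **Effect.** Section 11.1 gives the clinical outcome of the cost-effectiveness analysis as "in our study frequency of CH attacks during the last 4 weeks of the 100% stimulation period and the 30% stimulation period". Section 11.2 describes the same outcome as "increase in health status as measured by the CH attacks 4-weekly at 6 months of follow-up". Section 11.1 also states the expected direction: "we hypothesize that the high stimulation is associated with an increased effect".

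**Ratio.** Section 11.3 divides the cost difference (high minus low stimulation) by the effect difference taken in the same order. It then plots bootstrap replicates on a plane with incremental effectiveness on the horizontal axis and derives an acceptability curve over a range of ceiling ratios. The unit is described only as a cost per outcome rate.

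**Period.** Section 11.1 says: "The time horizon will be the same period as the follow-up period of the double blind part of the main study, 6 months". Costs come from a questionnaire covering 6 months.

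**Utilities.** Section 11.1 says that "outcomes for the economic evaluation study will be measured at pre-test before random assignment into groups (baseline), and at 6 months". Section 11.2 says that "The SF-36 will be completed monthly in the electronic diary", and that QALYs are the area under the curve through the measured time points.

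**Available data.** Section 4 says: "The patients will fill in an (electronic) diary during the whole study period". Section 7.2 already plans the attack frequency for every 4-week period of follow-up.

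**The concern.** There are three gaps, all in section 11.

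1. **Orientation.** The effect is a count of harm. The ICER, the plane and the acceptability curve work only if a larger effect is better. No sentence says that the count is to be reversed or expressed as attacks avoided.
2. **Window.** Attacks accrue throughout the blinded phase, as costs do. Setting 6 months of costs against the attacks of one 4-week window gives a ratio that is not a cost per attack avoided over the costed period. The vague unit in section 11.3 does not warn the reader of this.
3. **Utility time points.** Two utilities per patient and monthly utilities give different areas under the curve when stimulation is stepped up over the first two months. The plan supports both readings.

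At stake is whether two analysts working from section 11 would produce the same ratio, plane and QALY difference, and whether a reader would interpret the ratio correctly.

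Section 11.3 also defines its terms as annual cost and one-year effect, which conflicts with the 6-month horizon. That is a separate matter. The three gaps remain once it is aligned to 6 months, and the working below assumes 6 months.

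**Working it through.** **Inputs**
- A month is 4 weeks (section 7.1), so the 6-month blinded phase is six 4-week windows, or 24 weeks.
- Planning effect (section 16.4): a mean change of -9 attacks per week with 100% stimulation and none with 30%.
- The 100% arm has its full intensity for 4 of the 6 months (section 4).
- Incremental cost: the documents give none. EUR 1,000 is assumed for illustration. It cancels out of the factors below.

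The plan states no ICER, so there is none to reproduce. As a check on the planning effect, ln((26.42 - 9)/26.42) = ln(17.42/26.42) = -0.417, against the stated -0.42.

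**Step 1: orientation.** Take ICER = (Ci - Cc)/(Ei - Ec) with E as the raw 4-week count and equal baselines.
- Ei - Ec = -9 × 4 - 0 = -36.
- ICER = 1,000/(-36) = EUR -27.8.
- With E as attacks avoided, the denominator is +36 and the ratio is EUR +27.8.

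On the raw scale, an arm that costs more and prevents attacks plots as costlier and less effective. The acceptability curve is the probability that λ × ΔE - ΔC > 0, where λ is the ceiling ratio. With ΔE negative, that probability falls as λ rises.

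**Step 2: window.** Let f_k be the effect in window k relative to the last window, so f_6 = 1. Attacks avoided over 24 weeks are 36 × Σf_k. The last-window ratio (EUR 27.8), if read as a cost per attack avoided over the costed period, is too high by (1,000/36) ÷ (1,000/(36 × Σf_k)) = Σf_k.

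| Assumed time course | Σf_k | Attacks avoided | EUR per attack avoided |
|---|---|---|---|
| Constant over 6 months | 6.0 | 216 | 4.6 |
| 0.4, 0.7, then full | 5.1 | 183.6 | 5.4 |
| None in months 1-2, then full | 4.0 | 144 | 6.9 |
| Linear build-up to month 6 | 3.5 | 126 | 7.9 |
| None in months 1-3, then full | 3.0 | 108 | 9.3 |
| Last window only | 1.0 | 36 | 27.8 |
| Starts at twice its final size and wanes | 9.0 | 324 | 3.1 |

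**Step 3: utilities.** Assume a utility gain d that is half reached at month 1 and full from month 2.
- Monthly points (0, 0.5, 1, 1, 1, 1, 1) × d by the trapezoid rule: 0.25 + 0.75 + 1 + 1 + 1 + 1 = 5.0 d-months.
- Baseline and month 6 only: 0.5 × 6 = 3.0 d-months.
- The two-point area is 1 - 3.0/5.0 = 40% lower.

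**The case against.** **A reader might infer that the planned ICER simply has the wrong sign.** The documents do not support that. Section 11.2 calls the outcome a rise in health status, section 11.1 expects a larger effect with high stimulation, and section 11.3 labels the axis as effectiveness. Plotting an arm with fewer attacks as less effective would contradict this wording. This part of the objection stands. The defect is a missing conversion, and the sign reverses only if the count is entered untransformed.

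**A reader might infer that the plan overstates cost per attack avoided by 4- to 6-fold.** The plan never promises that quantity. Cost per unit reduction in the 4-weekly rate at 6 months is a coherent ratio, it is not inflated, and it uses the same window as the primary endpoint in section 7.1. The factors 4 and 6 belong to two assumed time courses and are not bounds. This also stands. It does not remove the need to name the unit, because the present wording does not show that cost and effect cover different periods.

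**A reader might infer that QALY gains will be understated by 40%.** Section 11.2 specifies monthly SF-36, sections 9.1 and 9.6 list it, and the area under the curve runs through the measured points. The 40% follows only if the sentence in section 11.1 takes precedence, and only under the assumed ramp. The contradiction itself remains.

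**Other limits.** Both arms receive the same implantation, so even the direction of the cost difference is unknown. The cost-utility analysis has no sign or window problem.

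**Conclusion.** The cost-effectiveness analysis cannot be reproduced from section 11 as written. A benefit is intended, but no rule turns a lower-is-better count into one, and the effect window (4 weeks) does not match the cost window (6 months).

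- **Sign:** on the planning effect, untransformed entry gives a denominator of -36 instead of +36. The plane is mirrored and the slope of the acceptability curve is reversed. This depends on literal programming, which the text permits but does not intend.
- **Window:** a factor of 4 if the effect is confined to months 3-6, 6 if it is constant, and about 1 to 9 across the other time courses tried. It applies only if the ratio is read as a cost per attack avoided over the costed period.
- **Utilities:** sections 11.1 and 11.2 contradict each other. Under the assumed ramp, the two-point reading gives 3.0 instead of 5.0 d-months.

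The consequence is confined to the economic evaluation. The primary efficacy analysis is not affected.

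**What to change.** 1. In sections 11.1 to 11.3, define the effect as attacks avoided (30% arm minus 100% arm), adjusted for baseline frequency and accumulated from the diary over the same 6-month blinded period as the costs. Use that sign for the ICER, the plane and the acceptability curve.
2. If the last-4-week measure is kept as a secondary ratio, label it as cost per unit reduction in the 4-weekly attack rate.
3. Amend section 11.1 to agree with section 11.2, so that QALYs use all monthly SF-6D values.
4. State in advance how incomplete diaries enter the cumulative count. Section 16.5 ends data collection for patients who switch to steroids, so some totals will be truncated.

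**Cost.** No new data are needed. The change is wording, some re-programming and a rule for incomplete diaries. The drawback is that the cost-effectiveness effect no longer shares the primary endpoint's window, and it takes in the 10-day run-in and the titration weeks, when the arms do not yet differ fully in stimulation. Keeping the secondary ratio in item 2 preserves the link to the primary endpoint.
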